Secondary Study Objectives	
The secondary objectives of this study are to:
 
 1) Compare total plaque volumes per-patient and per lesion as well as comparing different plaque type volumes to the IVUS reference standard and assess reproducibility of quantitative plaque measurements compared to the reference standard. 2) Perform exploratory analyses on plaque in previously stented vessels (protocol to allow up to 20% (50 patients) with one or two stented vessels vessels in this category. This can also include plaque proximal or distal to the stented vessel.
Hypotheses	The primary hypothesis of the study is that a deep-learning based automated method for segmenting coronary atherosclerotic plaques can quantify total plaque volume from CCTA with an acceptable level of agreement with IVUS measurements. The secondary hypothesis of the study is that CCTA-derived coronary models can accurately assess percent plaque burden as well as calcified, low attenuation, and fibrous plaque volumes with an acceptable level of agreement and repeatability compared to IVUS.
Population	Clinically stable patients with known CAD who have a CCTA showing stenosis in at least one major epicardial vessel of stentable/graftable diameter and in whom clinically-indicated IVUS is planned.
Study Design and Methods	This is a prospective, multi-center study. All patients who have a stenosis in at least one major epicardial vessel confirmed by CCTA, who have undergone FFR _{CT} analysis, and who are scheduled to undergo clinically indicated IVUS-guided invasive evaluation and/or treatment will be eligible for enrollment. Enrolling sites will have FFR _{CT} analysis incorporated when indicated into their standard evaluation of CCTA scans. Data collected will include CCTA and FFR _{CT} , full angiographic, and IVUS images, and if obtained, any other imaging or physiologic data including OCT, FFR, any NHPR (e.g., dPR, RFR, iFR, etc.), and pre-

REVEALPLAQUE Study Protocol Version 1.0 August 12th, 2021

	
and post-stent implantation invasive data. All non-invasive and invasive data collected will be obtained as clinical practice consistent with standard clinical care.
 
All details about cardiovascular testing and treatment (planned and actual) will be recorded at baseline. There will be no study required visits after the baseline invasive procedure.

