1. Compare total plaque volumes per-patient and per lesion as well as comparing different plaque type volumes to the IVUS reference standard and assess reproducibility of quantitative plaque measurements compared to the reference standard.
2. Perform exploratory analyses on plaque in previously stented vessels (protocol to allow up to 20% (50 patients) with one or two stented vessels in this category). This can also include

REVEALPLAQUE Study Protocol Version 1.0 August 12th, 2021

plaque proximal or distal to the stented vessel.

III. STUDY ENDPOINTS

III. A. Primary Endpoint

The primary endpoint is to assess the level of agreement between total plaque volume of a deep-learning based automated method for segmenting coronary atherosclerotic plaques, compared to IVUS, on a per-IVUS-pullback level.

III. B. Secondary Endpoints

Key secondary endpoints are:

Per pullback:

- Total plaque volume
- Percent plaque burden
- Calcified plaque volume
- Low attenuation plaque volume
- Fibrous plaque volume
- Segment involvement score (SIS)
- Adverse plaque characteristics (APC)

Per lesion:

- Total plaque volume
- Percent Plaque burden
- Calcified plaque volume
- Low attenuation plaque volume
- Fibrous plaque volume
- Minimum lumen area (MLA)
- Percentage area stenosis (%AS)
- Positive remodeling index

Per lesion/pullback:

- Reproducibility of all metrics above when quantified from different CCTA series
- Reproducibility of all metrics above when processing the same series twice (analyst and process variation)
- Exploratory analysis of necrotic core volume

IV. STUDY DESIGN

The REVEALPLAQUE study is a prospective, multi-center study designed to evaluate a deep-learning based automated method for segmenting coronary atherosclerotic plaques. All patients who have a stenosis confirmed by CCTA and FFR_{CT} available and who are scheduled to undergo IVUS will be eligible for enrollment. Enrolling sites will have FFR_{CT} analysis incorporated when indicated into their standard evaluation of CCTA scans. All sites will provide CCTA and FFR_{CT} images, full angiographic images, IVUS images, and if obtained, any other imaging or physiologic data including OCT, FFR, any NHPR (e.g., dPR, RFR, iFR, etc.), and pre- and post-stent implantation invasive data. All non-invasive and invasive data collected will be obtained as clinical practice consistent with standard clinical care.

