measures will be assumed to agree. Additionally, Pearson's correlation and paired t-test will be constructed to further describe the relationship between IVUS measurements and deep-learning based automated method for segmenting coronary atherosclerotic plaques from CCTA.

All secondary endpoints which are continuous (e.g., per lesion total plaque volume, per lesion calcium volume, per lesion low attenuation volume, per lesion non-calcified plaque volume, segment involvement score) will be similarly compared using a Bland Altman plot, Pearson's correlation and paired t-tests. Reproducibility will be estimated with Intra Class correlation (ICC).

IX. D. Sample Size

Approximately 250 subjects may be enrolled into this study.

From published data (Conte 2019), the maximum allowable difference between the measurements is 36 mm³. Assuming a standard deviation of 12 mm³, a sample size of 223 patients achieves 90% power to detect agreement when the mean is 8, confidence level of the (LoA) is 0.950 and the confidence level of the confidence intervals about the LoA is 0.950.

IX. E. Analysis Populations

All subjects who meet the study criteria, sign the written informed consent, and are enrolled in the study, and provide paired assessments of CCTA and IVUS measurements will be included in the analysis set.

X. DATA HANDLING AND QUALITY ASSURANCE

X. A. Completing and Signing Case Report Forms

This study will utilize eCRFs for the collection of all data. Data changes and corrections for any errors should be corrected within the eCRF. The audit trail will record all changes made, the date and time of the correction, the person making the change, and a reason for the change. The appropriate electronic signature will be provided by the investigator as indicated.

X. B. Clinical Data Management

The sponsor or designee will be responsible for the processing and quality control of the data. The handling of data, including data quality control, will comply with all applicable regulatory guidelines.

The training of clinical site personnel in eCRF completion will be the responsibility of the sponsor or designee. To ensure uniform data collection, Case Report Form Guidelines will be created to assist with eCRF completion. All site staff including investigators and research coordinators will undergo site initiation training to become thoroughly familiar with the protocol, case report forms, and with methods of data verification.

X. C. Archiving of Data

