Edit checks will be included in the study database to ensure that out of range values are checked prior to inclusion in the dataset. If unusual outliers are found in any of the individual study populations, an audit plan may be developed at that time.

XI. E. Clinical Events Committee

There will not be a Clinical Events Committee for this study.

XI. F. IVUS Core Lab

There will be an IVUS core lab responsible for annotating the angio images, IVUS images, and HeartFlow provided Paraview models according to predefined study workflows. These workflows will be the joint responsibility of HeartFlow and the core lab and will be approved by both parties prior to implementing any study case reviews. All imaging data and annotations will be housed in a centralized EDC database.

XI. G. HeartFlow Technology / Data Team

The HeartFlow technology / data team will be responsible for exporting the coronary models for all enrolled subjects via Paraview and uploading them into the EDC system for the core lab.

Following the core lab analysis and blinded to the core lab results, the technology/data team will have access to the x,y,z coordinates from the annotated Paraview models and will use those to determine the plaque volume from the deep-learning based automated method for segmenting coronary atherosclerotic plaques from CCTA. Further details will be included in the study manuals separate from the main protocol.

XII. FINAL REPORT

Following conclusion of the study, a final report from HeartFlow or its designee and may be distributed to all investigators. This final report will include all enrolled, eligible subjects.

REVEALPLAQUE Study Protocol Version 1.0 August 12th, 2021

XIII. REFERENCES

Taylor CA et al. Computational fluid dynamics applied to cardiac CT for noninvasive quantification of fractional flow reserve. J Am Coll Cardiol. 2013 <https://doi.org/10.1016/j.jacc.2012.11.083>

Thomsen C et al. Characteristics of high-risk coronary plaques identified by computed tomographic angiography and associated prognosis: a systematic review and meta-analysis. Eur Heart J. 2016 <http://doi.org/doi: 10.1093/ehjci/jev325>

Veros S et al. Coronary Atherosclerosis Imaging by Coronary CT Angiography: Current Status, Correlation with Intravascular Interrogation and Meta-Analysis J Am Coll Cardiol-CV Imaging 2011 <http://doi.org/10.1016/j.jcmg.2011.03.006>

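### Does the reproducibility objective require a repeat IVUS read, and must the protocol state that the core lab reads IVUS blind to the CCTA models?

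*Combined protocol and SAP*

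**What the plan says.** Secondary objective 1 (section II and the synopsis) is in part to "assess reproducibility of quantitative plaque measurements compared to the reference standard". The secondary hypothesis in the synopsis is that CCTA-derived models can assess plaque burden and plaque components "with an acceptable level of agreement and repeatability compared to IVUS".

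Section III.B lists two reproducibility endpoints, per lesion or pullback. The first varies the image data: "Reproducibility of all metrics above when quantified from different CCTA series". The second keeps the image data fixed and varies the processing: "Reproducibility of all metrics above when processing the same series twice (analyst and process variation".

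Section IX.C adds one sentence: "Reproducibility will be estimated with Intra Class correlation (ICC". It does not give the form of the ICC, the number of repeats or the values that enter it. No section mentions a second IVUS read, a second reader or a repeat pullback.

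On the reading itself, XI.F gives the core lab the task of "annotating the angio images, IVUS images, and HeartFlow provided Paraview models according to predefined study workflows". Those procedures are set jointly by sponsor and core lab and "will be approved by both parties prior to implementing any study case reviews". XI.G makes the sponsor's technology team responsible for "exporting the coronary models for all enrolled subjects via Paraview and uploading them into the EDC system for the core lab". That team then determines CCTA plaque volume after the core lab has finished and without sight of its results. XI.G leaves further detail to study manuals, and IX.A leaves the analysis methods to a SAP, calling section IX a brief overview.

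**The concern.** The objective and hypothesis seem to promise a comparison of two repeatabilities, CCTA against IVUS, while the endpoints supply repeats for one method only. Read that way, the study would report CCTA ICCs with no IVUS ICC to set beside them, and the repeatability half of the secondary hypothesis could not be tested. If IVUS is read once per pullback, the Bland-Altman, correlation and paired t-test results also cannot show how much of the scatter comes from reading IVUS and how much from CCTA.

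The second worry is independence of the reference. One core lab handles both the IVUS images and the sponsor's CCTA models, and the stated blinding runs in one direction only. If a reader traced IVUS with a CCTA-derived vessel wall in view, the two measurements could be drawn together and agreement would look better than it is.

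**Working it through.** **1. The plan's own figure.** Inputs from IX.D: allowable difference 36 mm³, mean difference 8, SD 12, 95% limits of agreement, 95% confidence intervals about them, 90% power, N = 223.

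- SE of a limit = SD × √(1/n + z²/(2(n−1))) = 12 × √(1/223 + 1.96²/444) = 1.375.
- Noncentrality at the near limit = (36 − 8 − 1.96 × 12)/1.375 = 4.48/1.375 = 3.26.
- Noncentrality at the far limit = (36 + 8 − 1.96 × 12)/1.375 = 20.48/1.375 = 14.89.
- Noncentral t with 222 df gives power 0.9004 at n = 223, the smallest n that reaches 0.90.

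The figure reproduces with 12 mm³ used as the SD of the paired CCTA-minus-IVUS difference. Such an SD ordinarily already contains IVUS reading error.

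**2. Does IVUS reading error alter the primary analysis?** The documents give no between-read SD, so take 2, 4 or 6 mm³ as assumptions.

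| Assumed IVUS read SD (mm³) | Share of variance if inside the 12 | SD of differences if added on top | Power at 223 if added on top |
|---|---|---|---|
| 2 | 4/144 = 3% | √148 = 12.17 | 0.84 |
| 4 | 16/144 = 11% | √160 = 12.65 | 0.60 |
| 6 | 36/144 = 25% | √180 = 13.42 | 0.20 |

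If the error is inside the 12, power is unchanged. If it came on top, power would fall, but a re-read of a subset would only describe that loss. It would not narrow the limits or restore power.

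**3. What the comparison wording can mean.**

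- *CCTA repeatability set beside IVUS repeatability.* This needs repeat IVUS data, and none is stated.
- *CCTA repeatability alone.* The endpoints deliver this, and the objective is loosely worded.
- *Each repeat CCTA quantification compared with the same IVUS reference, to see whether agreement holds up.* The endpoints deliver this too. III.B applies reproducibility to all the metrics listed above it, and IX.C compares the continuous secondary metrics with IVUS.

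Two of the three readings need no second IVUS read.

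**4. What a repeat IVUS read would add.** Assume 50 stored pullbacks read twice and an ICC of 0.90. With a one-way model, F₀ = (1 + 0.90)/(1 − 0.90) = 19. The bounds are F₀/F(0.975; 49, 50) and F₀ × F(0.975; 50, 49), each converted by (F − 1)/(F + 1), which gives 0.83 to 0.94. Precision would therefore be adequate, but relevance is limited. Re-reading one pullback captures reader variation. That roughly parallels processing one CCTA series twice, but has no counterpart for the different-series endpoint, where the image data themselves differ. Nor would it define what counts as acceptable repeatability.

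**5. Order of work at the core lab.** From XI.F and XI.G: the models are exported and uploaded; the core lab annotates them and the IVUS images; the sponsor's team, blinded to the core lab results, takes the coordinates from the annotated models and determines CCTA plaque volume. The coordinates locate the region to be measured on CCTA, so someone at the core lab must open the models. The volume for that region is determined only afterwards. What the protocol leaves open is what the models display and whether IVUS tracing is finished before they are opened.

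**The case for a change.** The best case for a change is that the text needs correcting on the first two readings: either the IVUS repeats are missing, or the objective claims more than the endpoints give. Repair looks cheap, because images are held centrally, a re-read involves no patient, and rewording costs nothing. A measured IVUS reading error would also help the sponsor explain wide limits if they occur.

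Part of this stands. The wording is loose, no repeat IVUS read is stated, and the protocol does not give the reading order. Single reads could not separate the two sources of variation.

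The rest goes too far. The protocol does not say that IVUS is read only once, nor which values enter the ICC, so a firm claim that the hypothesis cannot be tested is an inference. No objective asks for the error to be split between methods; the primary endpoint is agreement with IVUS as the reference. A re-read costs reader time and still leaves the different-series endpoint without a match. A sentence on reading order would record what the jointly approved workflows or the manuals may already contain, and the protocol shows no exposure of IVUS readers to the CCTA plaque volume.

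**Conclusion.** No change to the plan follows. The mismatch is one of wording in a secondary objective and hypothesis, and a competent SAP author would resolve it by stating that the ICCs describe repeat CCTA quantification, or that each repeat is compared with the same IVUS reference. Reading order is a matter for the core-lab workflows and is worth a query to confirm that IVUS contours, limits and measurements are complete before the models are opened.

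The effect on the planned figures is nil: N stays at 223 with power 0.9004, and neither the limits of agreement nor any planned estimate changes under a re-read, a rewording or an added statement.

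This rests on three assumptions: that the 12 mm³ already includes IVUS reading error, that the second reproducibility endpoint refers to CCTA series as its position suggests, and that the workflows or manuals fix the reading order. If they allowed readers to see CCTA wall or plaque contours while tracing IVUS, the blinding point would need to be reopened. Nothing in the documents shows that they do.
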